7.9.3.2. Laboratory Assessments

Unless otherwise specified, assessments during Cycle 1, Days 1, 8, 15, 22, 29, and 36 should be completed \pm 1 hour of the scheduled time; for other days during Cycle 1, \pm 3 hours; and for subsequent cycles and disease assessments, \pm 2 days. Details for laboratory assessments are provided in Section 11.5 and Section 11.6; details for PK, PD, flow cytometry, and biobanking are provided in Section 13.

Laboratory assessments include the following:

- CBC
- Chemistry panel
- Coagulation panel
- Urinalysis
- Serum pregnancy test for women of childbearing potential
- Blood for cell surface markers by flow cytometry or similar bioanalytical methods (see the Laboratory Manual for detailed instructions)
- PK (see the Laboratory Manual for detailed instructions)
- Cytokine/inflammation panel (see the Laboratory Manual for detailed instructions)
- ADA blood sample (see the Laboratory Manual for detailed instructions)
- Biobanking blood sample (optional; by specific subject consent)
- ECG, standard 12-lead
- RECIST 1.1 tumor assessment by CT/MRI (See Appendix A)
- Post-treatment fresh tumor biopsy (optional; by specific subject consent) to be examined by various immunohistochemistry assays for tumor-cell expression of SSTR2 and tumor- and immune-cell expression of proliferation and exhaustion markers, and transcriptomic analysis by Nanostring. The optional post-treatment fresh tumor biopsy should be performed between 12 and 21 days after the first dose of XmAb18087.
- NETSPOT gallium 68 dotatate PET/CT after the first cycle of treatment and, for subjects continuing to receive study drug, after every second cycle thereafter NETSPOT gallium 68 dotatate PET/CT should be performed after RECIST tumor assessment by CT/MRI has been completed. Refer to study manual for details on performing NETSPOT gallium 68 dotatate PET/CT.

Version 1.0 Page 63 of 145

7.9.3.3. End-of-Treatment Visit

Subjects will have their EOT visit at the end of the last cycle of treatment. If a subject terminates before the end of a cycle, the EOT assessments (Table 7, Schedule of Assessments) will be performed on the day of study termination.

Subjects with a positive ADA at study termination will be followed every 28 days (\pm 3 days), if feasible, until administration of another anticancer therapy, or until ADA levels return to baseline if results are available.

7.9.4. Post-treatment Follow-up Period (2 Weeks and 4 Weeks After EOT)

Subjects will have visits 14 days post-EOT and 28 days post-EOT. Assessments are as indicated in Table 7. Once these two visits have been completed, the subject will be considered as having completed participation in the clinical trial. If a subject enrolls into another trial or requires treatment before either of these scheduled visits, the visits may be performed earlier. If a subject is unable to return for any scheduled visits after the end of treatment, he/she will be considered as having completed study requirements at the end of treatment.

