11. ASSESSMENT OF SAFETY

Adverse event reporting will begin with the signing of the informed consent document (Screening) and will continue until the end of the subject's participation in the study: ie, until a subject has discontinued or completed the study.

Safety and tolerability assessments will include the following:

- AEs
- Vital signs
- PE findings
- Clinical laboratory safety assessments
- ECG parameters

Biomarkers of CRS (IL-2, IL-6, IL-8, IL-10, IFN- γ , IL-13, IL-1B, and TNF- α) will also be collected as additional safety information.

Details for management of hypersensitivity reactions, CRS, and neurologic toxicities are provided in Section 11.3.2, 11.3.3.3, and 11.3.3.4, respectively, as well as in Section 11.3.3 and Appendix C of this protocol.

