11.1.2. Recording of Adverse Events

AEs should be collected and recorded for each subject from the date the ICF was signed until the end of their participation in the study, ie, the subject has discontinued or completed the study. All AEs experienced by a subject, irrespective of the suspected causality, will be monitored until the event has resolved or stabilized, until any abnormal laboratory values have returned to baseline or stabilized at a level acceptable to the Investigator and Sponsor medical representative, until there is a satisfactory explanation for the changes observed, or until the subject is lost to follow-up.

Any new SAEs that are suspected to be related to study drug occurring up to 28 days after the last administration of study drug should be reported to ICON according to Section 11.1.5. Adverse events may be volunteered spontaneously by the study subject, discovered by the study staff during physical examinations, or by asking an open, nonleading question such as "How have you been feeling since you were last asked?" All AEs and any required remedial action will be recorded. The nature of AE, date (and time, if known) of AE onset, date (and time, if known) of AE outcome to date, severity, and action taken with the study drug because of the AE will be documented together with the Investigator's assessment of the seriousness on the AE and causal relationship to study drug and/or study procedure.

All AEs should be recorded individually unless, in the opinion of the Investigator, the AEs constitute components of a recognized condition, disease, or syndrome. In the latter case, the condition, disease, or syndrome should be named rather than each individual symptom. The date (and time, if known) that the Investigator or study site is first made aware of the AE (or any subsequent follow-up information is received) will be documented. The AEs will be coded using the current version of the Medical Dictionary for Regulatory Activities (MedDRA).

Each AE will be assessed by the Investigator with regard to the categories discussed in the sections below.

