11.1.4.1. Deaths

Should a death occur within the study period or within 28 days after the last administration of study drug (or until the subject initiates other anticancer therapy, whichever comes first), an AE form and an SAE form should be completed, detailing the AE that resulted in the death (death is an outcome, not an event). The SAE must be reported to the Medical Monitor within 24 hours. The report should contain a comment regarding the coinvolvement of progression of disease, if appropriate, and should assign main and contributory causes of death.

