11.1.5. Reporting Serious Adverse Events

The Investigator will review each potential SAE and evaluate the intensity and the causal relationship of the event to IMP. All potential SAEs will be recorded from signing of informed consent until the end of the subject's participation in the study: ie, the subject has discontinued or completed the study, except for the long-term follow-up period. During the long-term follow-up period, only SAEs that come to the attention of the Investigator and that the Investigator believes to have a reasonable causal relationship to the IMP will be reported.

The Investigator is responsible for reporting SAEs related to pembrolizumab to regulatory authorities per reporting guidelines.

The Investigator is responsible for providing notification to ICON of any potential SAE, whether deemed IMP-related or not, that a subject experiences during his/her participation in study within 24 hours of becoming aware of the event. ICON will provide the information to the Sponsor.

The initial SAE form should be completed and emailed to with the following information:

- Study number
- Subject number
- Gender
- Year of birth
- Name of PI and full clinical site address
- Name of the reporter
- SAE event term
- Details of SAE
- Criterion for classification as "serious"
- Study drug name, dose, and treatment start date
- Date of SAE onset
- Date of SAE first awareness (by Investigator or study site staff)
- Causality assessment

[figure not shown]
Version 1.0 Page 84 of 145

18 August 2020

ICON will request clarification of omitted or discrepant information from the initial notification. The Investigator or an authorized delegate is responsible for providing the requested information to ICON within 24 hours of the request.

Initial reports of SAEs must be followed up as soon as possible with detailed descriptions; this may include clear photocopies of other documents as necessary (eg, hospital reports, consultant reports, autopsy reports, etc.) with the study subject's personal identifiers removed. All relevant information obtained by the Investigator through review of these documents will be recorded and forwarded to ICON within 24 hours of receipt of the information.

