14.3. Study Endpoints

14.3.1. Primary Endpoints

The primary endpoints are as follows:

- Safety of (1) XmAb18087 monotherapy in MCC and SCLC, and (2) XmAb18087 and pembrolizumab combination therapy in MCC, as assessed by the following:
 - Incidence of treatment-emergent AEs (TEAEs)
 - Incidence of clinically significant changes in safety laboratory tests, PE findings, vital signs, and ECGs

Version 1.0 Page 99 of 145

- Incidence and severity of CRS
- Efficacy of (1) XmAb18087 monotherapy in MCC and SCLC, and (2) XmAb18087 and pembrolizumab combination therapy in MCC using RECIST 1.1 assessment of CT/MRI imaging, as well as aggregate data, for the following:
 - ORR
 - CR rate
 - PR rate

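### Protocol 7.9.4 can close general adverse-event collection at end of treatment for subjects who cannot return, so part of the scheduled 28-day follow-up goes uncollected

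*Protocol*

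**What the plan says.** Protocol 7.9.4 schedules visits 14 and 28 days after EOT. For those who attend, "Once these two visits have been completed, the subject will be considered as having completed participation in the clinical trial". Those who cannot attend are treated differently: "unable to return for any scheduled visits after the end of treatment, he/she will be considered as having completed study requirements at the end", meaning at EOT, and nothing further is required.

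Table 7 schedules AE monitoring at EOT and at both post-EOT visits. Section 11 ties the end of AE reporting to status, not to a number of days: it "will continue until the end of the subject's participation in the study: ie, until a subject has discontinued or completed the study". Section 11.1.2 repeats that rule for recording AEs, and 11.1.5 applies it to SAEs in general.

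Four routes stay open whatever the visit attendance:

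- **Related SAEs.** 11.1.2 keeps "Any new SAEs that are suspected to be related to study drug occurring up to 28 days after the last administration of study drug".
- **Deaths.** 11.1.4.1: "Should a death occur within the study period or within 28 days after the last administration of study drug", an AE form and an SAE form are due. Starting other anticancer therapy ends this period early.
- **Late related SAEs.** 11.1.5: "During the long-term follow-up period, only SAEs that come to the attention of the Investigator" and are thought causally related are reported.
- **AEs already begun.** 11.1.2 and 11.1.6 follow them to resolution, stabilization, explanation or loss to follow-up.

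The remote contacts at 6 and 12 months (7.9.5) ask about progression and survival, not AEs. TEAE incidence is a primary safety endpoint (14.3.1), and the TEAE definition (14.6; SAP 11.1) has no upper time limit. SAP 6.3 sets the final analysis after every subject has had the 28-day post-EOT visit.

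**The concern.** The length of AE observation depends on whether the subject can come back. If 7.9.4 counts as completion for the purposes of Sections 11 and 11.1.2, a subject who attends is observed for any AE to 28 days after EOT. One who cannot attend is observed after EOT only through the four routes above.

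Two groups of events fall outside those routes: new non-serious AEs, and new non-fatal SAEs not suspected to be related. The first group matters because an adverse event of specific concern (AESC, 7.8) need not be serious. Grade 3 thrombocytopenia lasting at least 7 days is an example.

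Such a subject stays in the safety population, which requires only one infusion, so a missed event lowers the numerator and leaves the denominator unchanged. Any error in planned TEAE incidence is therefore downward. The subject may also appear in the disposition listing without any sign that safety follow-up was cut short.

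**Working it through.** The documents state no figure on this point, so there is none to reproduce. The check is a reading of the rules, then window arithmetic, then a sensitivity range.

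**1. What is collected after EOT for a subject who cannot return**

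| Event | Governing section | Collected? |
|---|---|---|
| AE already under way at EOT | 11.1.2, 11.1.6 | Yes, unless lost to follow-up |
| New SAE suspected related, to 28 days after last dose | 11.1.2 | Yes |
| Death in that period, before other anticancer therapy | 11.1.4.1 | Yes |
| Later related SAE known to the investigator | 11.1.5 | Yes |
| New non-fatal SAE not suspected related | 11.1.5 stops at completion | No route |
| New non-serious AE, including AESC-type events | 11 and 11.1.2 stop at completion | No route |

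**2. Windows for a subject who stops after one full cycle**

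Inputs: last XmAb18087 dose on Day 36 (Tables 2 to 4). EOT is taken as about Day 38 to 42, an assumption from the Day 40 ± 2 assessment and the 42-day cycle.

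- The related-SAE and death window ends on Day 36 + 28 = 64. That is 64 − 42 = 22 to 64 − 38 = 26 days after EOT, so it covers 22 to 26 of the 28 post-EOT days.
- The 28-day visit falls on Day 38 + 28 = 66 to Day 42 + 28 = 70. That is 30 to 34 days after the last dose, so the two windows do not end together.
- General AE time falls from 66–70 days to 38–42 days. The calendar loss is 28/70 = 40% to 28/66 = 42%. This is a share of time, not of events.

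Under 7.9.3.3, a subject who stops mid-cycle has EOT assessments on the day of termination, so the cut comes earlier.

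**3. Possible size**

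Let f be the share of subjects unable to return, and q the chance that, in such a subject, a given event first starts in the 28 days after EOT. Neither is in the documents. Assumed ranges are f = 5% to 30% and q = 5% to 40%.

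Percentage points lost = 100 × f × q, before adding back the SAEs and deaths still reported:

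- f = 0.05, q = 0.05: 0.25
- f = 0.10, q = 0.20: 2.0
- f = 0.30, q = 0.40: 12

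For any TEAE, only subjects with none on treatment can change the count. Let p be the share already with a TEAE (assumed 80% to 95%), and let q apply to the rest. Points lost = 100 × f × (1 − p) × q:

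- f = 0.10, p = 0.95, q = 0.20: 0.1
- f = 0.30, p = 0.80, q = 0.40: 2.4

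**4. What remains under the SAP**

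SAP 5.1 reports 4 enrolled subjects (2 in Part A, 2 in Part C) and listings only, so no incidence is estimated. SAP 11.1 still flags TEAEs. SAP 8.1 still lists dates and reasons for end of treatment and end of study, but has no item for 28-day follow-up. SAP 6.3 waits for a visit that a subject covered by the 7.9.4 rule never has.

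**The case against.** **The link is an interpretation.** Section 7.9.4 says attendees complete participation in the trial, but says non-returners complete study requirements. Sections 11 and 11.1.2 use a third wording. The AE cut-off is therefore not stated outright. This stands as an ambiguity. It does not remove the problem: calling the subject discontinued ends AE collection too, and no section tells a site to keep collecting.

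**Much is retained.** A reader might infer that these subjects contribute nothing after EOT. The documents do not support that, as the four open routes show. Toxicity that already prevents a return is recorded and followed. Section 8.8 also asks for post-treatment evaluations within 4 weeks of the last XmAb18087 dose, and 11.3.3.3 keeps subjects with recurrent Grade 3 or any Grade 4 infusion reaction on follow-up for 4 weeks. These passages show intent, but they give no means of collection when a subject cannot attend.

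**Who fails to return is unknown.** A reader might infer that the sickest subjects are the ones cut off. That is plausible in relapsed or refractory disease, but the documents give no reasons for non-return, so it remains inference.

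**Calendar time is not risk.** A reader might also infer that incidence falls in proportion to the 40% to 42% of days lost. That would need roughly constant risk, whereas Section 5.1.7 expects cytokine release syndrome mainly after the first dose. The AESC rates in 7.8.2 cannot supply the missing input either: they describe a different measure over a toxicity follow-up period that is not defined.

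**The trial stopped early.** With 4 subjects and no rate estimated, the bias argument applies to the protocol's planned endpoint and not to a reported result. This stands.

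**Conclusion.** The point holds in a limited form. On its most natural reading, 7.9.4 with Sections 11 and 11.1.2 leaves two kinds of post-EOT event without a collection route in subjects who cannot return: new-onset non-serious AEs and non-fatal SAEs not suspected to be related.

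The effect on planned TEAE incidence can only be downward. Its size cannot be derived from the documents. It is probably small for any-TEAE incidence and larger for less common or late-onset events; Appendix D notes that immune-related events may arise up to several months after pembrolizumab, which concerns Part B. The ranges in the working rest wholly on assumed f, q and p and do not subtract the retained SAEs and deaths.

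Under the current SAP the consequence is confined to the completeness of the AE and disposition listings for 4 subjects, none in Part B. The documents do not say whether any of the 4 failed to return. This is a cheap improvement, not an error that overturns a conclusion.

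**What to change.** - **Protocol 7.9.4.** State that if a post-EOT visit cannot be attended, AEs, SAEs and vital status through 28 days after EOT are collected by telephone or from medical records, and that the subject is recorded as not having completed post-treatment follow-up, with the reason.
- **Protocol 11.** State that AE collection runs for this fixed period whatever the visit attendance or completion status.
- **Reconcile** 7.9.4, 11, 11.1.2 and 11.1.4.1, which mix windows counted from EOT with windows counted from the last dose. Bring SAP 6.3 into line so that the final analysis does not wait for a visit that may never occur.
- **SAP 8.1.** Add a column showing whether 28-day safety follow-up was completed.

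The cost is a sentence in each of two protocol sections, the reconciling edits and one listing column. In operation it means one or two extra telephone contacts for subjects who cannot attend, by a means sites already use at 6 and 12 months.

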7.9.5. Long-Term Follow-up Period (6 and 12 Months After EOT)

Subjects will be contacted by site staff by telephone, email, or mail at 6 and 12 months after their active participation in the study ends to gather information about disease progression and survival. Completion of the long-term follow-up period is not required for a subject to be considered as having completed the clinical trial.

7.10. Discussion of Study Design

This is a Phase 1b/2, multiple-dose study designed to describe safety and efficacy, and to assess PK and immunogenicity of XmAb18087 monotherapy and in combination with pembrolizumab in subjects with metastatic MCC or locoregional MCC that has recurred after locoregional therapy with surgery and/or radiation therapy, and XmAb18087 monotherapy in subjects with extensive-stage SCLC that has progressed after standard therapies.

Part A of the study will enroll safety run-in cohorts of subjects with advanced MCC that has progressed after treatment with standard therapies to confirm the safety and tolerability of XmAb18087 monotherapy administered IV with weekly step-up dosing for 42-day cycles. Additional subjects will be enrolled into an expansion cohort and will receive XmAb18087 monotherapy using the RD identified following the safety run-in.

Part B of the study will enroll safety run-in cohorts of subjects with advanced MCC not previously treated with anti-PD1 or anti-PDL1 agents, and for whom pembrolizumab as a single agent is indicated, to confirm the safety and tolerability of XmAb18087 in combination with pembrolizumab. Subjects will receive step-up IV dosing of XmAb18087 on Days 1, 8, 22, 29, and 36, and IV dosing of pembrolizumab on Day 15 of each 42-day cycle. Additional subjects will be enrolled into an expansion cohort and will receive XmAb18087 plus pembrolizumab combination therapy using the RD identified following the safety run-in.

Enrollment into the first safety run-in cohort of Part B (Cohort 1B) may begin after the first safety run-in cohort in Part A (Cohort 1A, one dose level higher than Cohort 1B) has completed the first cycle and the regimen has been demonstrated to be tolerable.

Version 1.0 Page 64 of 145

Part C of the study will enroll safety run-in cohorts of subjects with extensive-stage SCLC that has progressed after treatment with standard therapies to confirm the safety and tolerability XmAb18087 monotherapy. The safety run-in will follow the same cohort schema as described for Part A to identify a RD for expansion in SCLC. Additional subjects will be enrolled into an expansion cohort and will receive XmAb18087 monotherapy using the RD identified following the safety run-in.

Enrollment into Part C may begin concurrently with Part A.

7.10.1. Risk/Benefit and Ethical Assessment

XmAb18087 has been characterized through an extensive program of in vitro and in vivo testing which demonstrates that the drug binds CD3 and SSTR2 and is active against SSTR2⁺ cells and tumors. The pharmacology and toxicology of the drug have also been studied in numerous experiments using cynomolgus monkeys, the relevant species for a CD3-directed bsAb. Pharmacology results show that XmAb18087 activates T cells, and toxicology results, as well as results from the first 42 subjects dosed in the XmAb18087-01 trial, indicate that the drug can be administered safely within the careful program of prophylactic medication, frequent subject assessment, and close observation that the XmAb18087-02 clinical trial protocol describes. Given that Part A and Part C of the XmAb18087-02 trial are being conducted in subjects with advanced cancer for which there is no effective available therapy, the sponsor believes that the administration of monotherapy under the auspices of this clinical study is ethical.

Pembrolizumab (Keytruda[®]) is approved for the treatment of adult and pediatric patients with recurrent locally advanced or metastatic MCC. Given that the combination of XmAb18087 and pembrolizumab will be administered to this patient population within a careful program of frequent subject assessment and close observation, the Sponsor believes that the proposed combination therapy portion of the clinical study is ethical.

7.10.2. Termination of Study

If the Investigator or the Sponsor becomes aware of conditions or events that suggest a possible hazard to subjects should the clinical study continue, the clinical study may be terminated after appropriate consultation among the involved parties. The clinical study also may be terminated at the Sponsor's discretion, also in the absence of such a finding.

Conditions that may warrant termination of the clinical study include, but are not limited to:

- The discovery of an unexpected, relevant, or unacceptable risk to the subjects enrolled in the clinical study.
- Failure to enroll subjects at the required rate.
- A decision of the Sponsor to suspend or discontinue development of the IMP.

Should the study be terminated and/or the site closed for whatever reason, all documentation pertaining to the study and IMP must be returned to the Sponsor. Any actions required for assessing or maintaining study-subject safety will continue as required, despite termination of the study by the Sponsor.

Details for study termination due to AESC are provided in Section 7.8.2.

Version 1.0 Page 65 of 145

